## **A1. BACKGROUND AND SIGNIFICANCE**

**Depression and Veterans' health, functioning, and quality of life.** Depression prevalence among OEF/OIF Veterans is high (e.g., 59% screened positive; Seal et al, 2008), with increasing rates among this cohort of Veterans over the past few decades (Seal, 2009), making depression the most prevalent mental health concern in the VA. Although some recover quickly, the majority experience recurrent and often chronic depression (Whiteford, 2013). By the third episode, a person with a history of depression is 90% likely to experience another episode, highlighting the critical role of early intervention and care. Depression is a vastly heterogeneous syndrome (Monroe & Harkness, 2012) primarily characterized by low mood and anhedonia. Among Veterans, depression is a comorbid condition that complicates the course of PTSD and TBI recovery. Depressed people are 30 times more likely to commit suicide than are healthy individuals (Joiner, 2010) and 5 times more likely to abuse substances. The prevalence of depression and its associated morbidity and mortality make care for depression a high priority in the VA (DVA/DoD, 2016).

**Depression care in the VA.** Cognitive behavioral psychotherapies and psychotropic medications are recommended by VA practice guidelines and are available as first line treatments for depression, yet Veterans often do not **engage** (i.e., initiate, adhere) in offered care. Despite great efforts to promote evidence-based treatments (EBTs) as the gold standard of care for depression and to increase access to mental health care in the VA (Mott, 2014), **any mental health care utilization among veterans continues to be low** (i.e., 18.5-27%; Burnam, 2009; Mott, 2014). Low utilization of care highlights a major gap in the guidelines for depression care in the VHA. VA clinical practice guidelines for the management of major depressive disorder (MDD; VHA/DoD, V3, 2016) omits any discussion of the management of patients who require clinical care but disengage. Given the sequelae of untreated depression, it is paramount to both identify those at risk for dropping out of care and develop strategies for management of patients that prematurely disengage from traditional care.

**Barriers to care.** To better understand patterns in access to care, Levesque's framework proposes that patient characteristics interfere with successful treatment utilization alongside system barriers (see Levesque et al, 2013). Relevant patient characteristics that ultimately lead to care access are ability to perceive, seek, reach, pay, and, finally, **engage in care** (see Figure 1). These abilities map onto a process that incorporates identifying health care needs, perception of needs and desire for care, healthcare seeking and reaching, health care utilization, which increasingly lead to health care consequences.

Empirical research has shown consistently that lack of perceived need for treatment is a major barrier to care. Level of illness severity may impact perceived need; in one study, low perceived need was more often a reason for not seeking treatment among individuals with mild (57.0%) or moderate (39.3%) than severe (25.9%) disorders (Mojtabai et al, 2011). Unfortunately, depression is related to negative health outcomes and poor functioning across severity levels, even when subthreshold symptoms are present (Boulenger, 2004). When need for treatment is present, emotional and evaluative barriers become more powerful in interfering with treatment engagement (Mojtabai et al, 2011). In depression especially, withdrawal behaviors likely stem from low emotional awareness which is often linked to maladaptive coping and low self-efficacy (Good, Dell, & Mintz, 1989; Schwarz & Clore, 1983, 1996). Military training may also impact future treatment seeking and adherence by instilling emotional control (Nash, Silva, & Litz, 2009) and valuing the ability to control emotions under stress to promote survival and mission completion. Beliefs that promote emotional avoidance and self-reliance may inadvertently delay treatment seeking (MacKenzie, Gekoski, & Knox, 2006; MacKenzie, Knox, Gekoski, & Macaulay, 2004). **Despite poor awareness and avoidance contributing to depression treatment engagement, few interventions have targeted these mechanisms to improve care. Given the low care utilization, pretreatment interventions may help patients to understand their health concerns and facilitate engagement by providing tools for treatment planning.** Pre-treatment interventions could also include practical and emotional support to further drive engagement. In a recent meta-analysis, both practical and emotional support played roles in treatment engagement (DiMatteo, 2004).

**The use of analytics in understanding patient phenotypes.** Health care has lagged behind other industries in the use of advanced analytics to drive performance. The VHA's EHR provides a unique opportunity for efficient, large-scale investigation of potential clinical markers or patient phenotypes. Ideally, such studies will employ advanced analytics like machine learning to define relevant constructs. The application of analytics tools has enabled accurate and efficient determination of longitudinal outcomes, enabling existing EHR data to be applied to clinical research. Machine learning, for example, was used to predict suicidal ideation among adults recently discharged from psychiatric inpatient or emergency room settings (Cook et al, 2016). Preliminary work has been conducted to improve methods of estimating use of EBP. Shiner and colleagues (2012) evaluated administrative data and text notes for patients newly enrolling in six VHA outpatient PTSD clinics in New England during the 2010 fiscal year. They developed machine learning algorithms that mimic human raters in classifying note text and found that 6.3% of their study population received at least one session of evidence-based psychotherapy during the initial 6 months of treatment. (Shiner et al, 2012). **The current CDA will build on prior work by using machine learning to define Veteran patient phenotypes associated with risk for not engaging in evidence-based care when the EHR indicates evidence of probable depression.**

**Overcoming treatment barriers through self-monitoring.** Prior work to overcome treatment barriers focused on improving patient motivation, however, attempts at increasing treatment initiation via single session motivational interviewing strategies have been largely unsuccessful. Although depression is linked to motivational deficits, the mechanism by which care is interrupted may be diverse based on patients' needs and characteristics. The literature suggests variability in perceived need and cognitive and emotional barriers once need is identified. Furthermore, the pre-treatment process is dynamic, likely involving various barriers depending on time lag between referral and treatment onset, ultimately limiting self-efficacy and ability to engage in care (Levesque et al, 2013).

Results from large national trials like the Sequenced Treatment Alternatives to Relieve Depression (STAR\*D) Study found that management of depression was facilitated by active monitoring of symptoms (Rush et al, 2004). This principle has been a key component to integrated care treatment trials including Re-Engineering Systems of Primary Care for PTSD and Depression in the Military (RESPECT-Mil), Behavioral Health Laboratory (BHL), and Translating Initiatives in Depression into Effective Solution (TIDES), the main VA and DoD programs (Rush et al, 2004; Tew et al, 2010; Engel et al, 2008; Rubenstein et al, 2010). **Systematic symptom measurement through self-monitoring may give patients a new role in their care (Valenstein et al, 2009).** For example, Guo et al. (2015) conducted an RCT in which patients were either monitored using a DSM checklist or not monitored. Not only did the monitored group have greater improvement in symptoms, there was evidence for better treatment management (Guo et al, 2015). Patients who regularly complete standardized assessments may become knowledgeable about their symptoms and depression and become comfortable assessing their own symptom trajectory, all key aspects of disease self-management. Symptom reports also have been an integral part of CBT for depression. A growing body of evidence supports the benefits of regular monitoring with feedback to patients to improve outcomes. For example, both theory and research suggest that mood labeling (the ability to identify and categorize one's moods) rather than ambiguous monitoring (a tendency to scrutinize and focus on one's moods) has value in the self-regulation of behavior (Swinkels & Giuliano, 1995). It follows that self-management strategies may help both non-engaged and newly referred patients: non-engaging patients understand their need for care and may later elect to initiate treatment, while newly referred patients experience increased ability to engage. Active engagement in care increases a sense of self-efficacy. Furthermore, data that are obtained from the period prior to entering treatment can help patients readily guide treatment planning.

**eHealth platforms have the potential to provide dynamic pre-treatment support.** eHealth/mHealth interventions are tools or treatments, typically behaviorally based, that are operationalized and transformed for delivery via the internet or mobile platforms (Ritterband et al, 2009). In the VA smart phone-based tools and interventions have been explored as a potential adjunct to therapy, given their ease of use in any context in helping with treatment initiation, adherence, and monitoring for chronic illness. In fact, patients in all age groups have indicated greater than 50% interest in using a mobile application daily to monitor their mental health conditions (Torous et al, 2014). Even among homeless Veterans, 89% had a mobile phone (one-third were smartphones), and 76% used the Internet. Among those with a mobile phone, 71% used text messaging. Nearly all respondents (93%) were interested in receiving mobile phone reminders about upcoming medical appointments, and a similar proportion (88%) wanted mobile phone outreach asking if they would like to schedule an appointment if they had not been seen by a health provider in over a year (McInnes, et al., 2014). **Mobile**

capabilities may significantly improve patient compliance with treatment (Reger et al, 2013). Symptom monitoring during the treatment process can also be significantly enhanced via mobile applications and adherence to real-time self-monitoring may be enhanced when conducted via mobile phone or a similar handheld device. Many patients who complete paper self-monitoring, do so retrospectively (Matthews, Doherty, Coyle, & Sharry, 2008), and this process is more prone to error (Shiffman, Stone, & Hufford, 2008). Conversely, mobile phone monitoring enables interventionists to see precisely when the ratings were taken. Daily ambulatory monitoring of symptoms using smartphone software applications was also feasible and valid way of assessing psychotic phenomena (Palmier-Claus et al, 2012), suggesting this as a viable method for even the most severe patients. **We propose to leverage an eHealth platform to provide a dynamic pre-treatment mechanism to help patients stay engaged with prescribed mental health care for depression through self-monitoring and emotional and practical support.**

**Gaps Addressed.** This CDA will address multiple gaps in our understanding of how to optimize depression care. Although studies have examined barriers to mental health treatment at a population level, this is the first study to apply machine learning algorithms to a large body of data in order to identify discrete individual patient phenotypes associated with poor treatment engagement (Aim 1). Second, despite past efforts to identify barriers to treatment, little work has focused on trying to tailor interventions to address barriers to treatment proactively among individuals most at risk of failing to engage. This is the first attempt at designing an intervention that uses individualized feedback (i.e., measurement based care)—shown to help both with treatment adherence and efficacy—to create a patient level support system from the moment of referral to mental health care to the initiation of treatment (Aims 2 and 3)—a period that is known to be associated with disengagement.

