##### **A4a. Aim1.**

Study/Design overview: I will conduct a secondary data analysis of EHR data. This will be a retrospective cohort study to identify patient phenotypes associated with lack of treatment engagement for depression. This aim was developed based on empirical evidence and Levesque's Framework (2013) (Figure 1), which proposes that patient level factors impact health care utilization and outcomes. Our proposed analyses will focus on data available from EHRs (observed variables). Based on this framework, patient level factors may impact the process of initiating care along a continuum of identifying health care needs, perception of needs and desire for care, health care seeking, and reaching. These factors will be captured through proxy measures available in the EHRs. For example, based on the literature reviewed in the background and my own preliminary work, identification of care needs, perception of needs, and desire for care are all a function of depression severity, gender, and ethnicity, such that higher severity, female gender, and white race tend to all be associated with higher levels of perception of needs and openness to mental health care. Specifically, for this study, we plan to use the 88,456 OEF/OIF Veterans with a Patient Health Questionnaire 9 (PHQ9)  $\geq 10$  (indicative of probable depression) randomly split into sub-samples to accommodate our goals. I plan to develop Aim 1 in two related stages. (Stage 1) First, I will develop patient profiles using conventional logistic regression analysis. In this analysis, the estimated 88,456 OEF/OIF Veterans with a PHQ9  $\geq 10$  will be randomly split into development and validation sub-cohorts. Estimates extracted from the development sub-cohort will be used to compute risk scores, with ROC analysis performed to determine a presumed optimal cut-off score. These profiles and cutoff score will be evaluated for prediction accuracy on the validation sub-cohort. (Stage 2) To evaluate the results from Stage 1, patient profiles will then be developed and validated with machine learning paradigm on the 88,456 OEF/OIF Veterans with a PHQ9  $\geq 10$ . Use of this approach is based on the fact that while various characteristics have been investigated in the past in an attempt to identify patients' likelihood to use services, we have yet to apply advanced machine learning techniques to the rich data available in the EHRs to define a profile of patients at risk to not engage in mental health care for depression. Ultimately, our goal is to identify the best fitting model in terms of prediction performance and interpretation, whether by logistic regression analysis or machine learning methods. The risk scores identified in this Aim will be utilized to recruit patients for Aims 2 and 3. While the models developed for Aim 1 will be based on "observed" variables only, there may be important "unobserved" variables we are not able to include. Methods related to this potential concern are described below in the Analysis Plan section.

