
Table 1. List of variables extracted from electronic medical record data.

Observed Independent Variables	
Demographics	Age, gender, race/ethnicity, marital status, service connected disability.
Non-psychiatric illness	Elixhauser measure
Depression diagnoses	ICD-9 Depression Codes e.g., 296.2-296.36; 293.83; 309.0.
Anxiety Disorders/ PTSD diagnoses	ICD-9 CM codes for Anxiety and Stress-related conditions e.g., 293.84; 309.24; 309.28; 309.81; 300.00-300.09.
Serious Mental Illness diagnoses	ICD9-CM codes for Bipolar Affective Disorder Type 1, Schizophrenia e.g., 293.81-293.83; 296.40-296.7; 295.40-295.90; 296.56-293.83.

Alcohol/Substance Use Disorder Diagnoses	ICD9-CM codes for Alcohol, Amphetamine, Cocaine, Inhalant Use Disorders: 291.89-304.40.
Depression severity	PHQ-9 items and scores
Depression chronicity	Time from first to last ICD9 code or time between elevated PHQ9s
Anxiety severity	GAD-7 items and scores
PTSD severity	PCL-5 items and scores
Affective characteristics	PCL-5 clusters C (emotional avoidance), D (negative mood and cognitions), E (arousal and reactivity)
Somatic difficulties	Somatic factor of the PHQ9 (e.g., fatigue, sleeping difficulties)
Instrumental Variables	
Distance to the VA	e.g., GIS tracking, zip code mapping
System approachability	Is the mandatory annual depression screen completed in the past year?; Does pt have PCMH routine check in over the past two years?
Ability to reach VA	Has available transportation/eligible for VA transportation; full time or multiple jobs
Family support	Asian and Black race (as proxy) have been associated with increased social stigma of mental illness, including lack of family/friends support to seek mental health services
Beliefs about care	Gender and race have been associated beliefs about MH care
Unobserved Variables	
Transportation availability	These variables have been repeatedly identified in the literature as barriers to mental health treatment. We will not have this information available in the structured data.
Employment	
Child or family care	
Outcome Measure (Dependent Variable)	

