Treatment initiation	A primary or secondary stop code showing a visit in mental health (with a psychologist or psychiatrist) or primary care AND an ICD9 for depression diagnosis.

Sampling plan and data extraction and processing:

**Data source and cohort selection.** We will use data from the VA Corporate Data Warehouse (CDW), a centralized data repository which contains electronic medical records of all Veteran patients who receive care through the VHA. The patient cohort (N = 88,456) used for completion of Aim 1 includes 1) OEF/OIF Veteran patients with a PHQ9  $\geq$ , 2) who were not already in treatment for depression prior to this PHQ9 assessment, 3) were never diagnosed with bipolar, personality, psychotic, and pervasive developmental disorders to be consistent with the National Committee on Quality Assurance measure of quality of care, HEDIS (HEDIS, 2018), as well as substance dependence or patients who are in treatment for substance related disorders at the time of recruitment. The exclusion criteria are based on the fact that the presence of these disorders may result in divergent treatment practices compared to unipolar depression in the absence of these conditions. Our primary outcome, treatment initiation, is conceptualized as a combination of service encounters with specialty mental health (psychologists, psychiatrists) or primary care providers charted into the patients' VHA medical records (excluding assessments) that were associated with any depressive disorder diagnosis. Our data are already IRB exempt, R&D and DART approved, and have already been extracted.

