#### A4b. Aim 2.

Study/Design overview: This aim is phase 1 focusing on the formative development of the eHealth intervention using a human-centered design (see Appendix 2). *Guiding the development of this Aim (and Aim 3) will be Levesque’s Framework which proposes that patient’s ability to engage is at the core of successful health care consequences (i.e., outcomes). Therefore, the focus will be on providing patients the mechanism to initiate treatment. This will be done via active self-monitoring and specific labeling of depression symptoms, as well as via emotional and practical support. Based on this framework, the process by which behavior change about treatment is activated is by helping patients more clearly identify health care needs (i.e., via symptom monitoring) help rectify perception of needs (by providing feedback on symptoms, whether they are elevated and a provider should be contacted), helping with care seeking and reaching (i.e., sending provider contact information and sending reminders).*

Sample: This aim will be achieved by involving 10 stakeholders (patient n = 6 and provider n = 4). Patients will be selected based on risk scores generated in Aim 1 and the following inclusion/exclusion criteria. Patient and provider input will be used to revise intervention content.

Table 2. Patient inclusion/exclusion criteria for Aims 2 and 3.

Inclusion criteria:

- OEF/OIF Veteran: high prevalence of depression in this population and generalizability across adult ages
- PHQ9 $\geq 10$ ; DSM-5 criteria for major depressive disorder will be used to extract an MDD diagnosis.
- No gender or minorities will be excluded from this study; all ages will be included.

Exclusion criteria:

- Current/Past Bipolar disorder and Current Psychotic disorder: to avoid potential exacerbation from treatment for depression
- Alcohol Use disorder or Substance Use disorder: Depression treatments cannot reverse the adverse effects of substances on mood, and therefore impact on adherence and treatment characteristics may be confounded

- Other current severe or unstable, psychiatric and medical disorders that necessitates clinical management that can confound results (e.g., cancer [in chemotherapy], suicidality, recent hospitalization [medical/surgical] for which recovery overlaps with study onset and duration, open skull/brain injury, moderate to severe TBI)
- Moderate to severe cognitive impairment (SLUMS  $\leq 20$  and/or diagnosis in medical record)

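### Aim 1 counts Veterans evaluated and found not depressed as non-engaged, and undated depression codes among the predictors let the selection score partly predict the absence of a code

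*Protocol*

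**What the plan says.** The background (Protocol A1) gives the Aim 1 target as "risk for not engaging in evidence-based care when the EHR indicates evidence of probable depression" and the gap to be filled as the "management of patients who require clinical care but disengage".

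- **Entry (A4a).** An OEF/OIF Veteran needs a PHQ-9 of 10 or more, no current depression treatment and none of the listed excluded disorders. The protocol calls such a score probable depression. No diagnosis is required.
- **Outcome (A4a, Table 1).** Treatment initiation is a "visit in mental health (with a psychologist or psychiatrist) or primary care AND an ICD9 for depression diagnosis". The cohort text agrees: assessments are left out, and only encounters "that were associated with any depressive disorder diagnosis" count. Initiation is judged at 3, 6 and 12 months from the PHQ-9 date.
- **Predictors (A4a, Table 1).** The list includes "ICD-9 Depression Codes", with no look-back window. Depression chronicity may also be measured from first to last code.
- **Use (A4a, A4b).** An ROC cut-off is set on the score, and the score selects patients for Aims 2 and 3. Table 2 lists among its inclusion criteria that "DSM-5 criteria for major depressive disorder will be used to extract an MDD diagnosis". Recruitment is mainly through mental health consults and provider referral.

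**The concern.** The entry rule and the outcome rule refer to different populations. A positive PHQ-9 admits a Veteran, but only a depression code lets that Veteran succeed. Someone who attends, is evaluated and turns out not to have a depressive disorder is recorded as lacking engagement at all three time points, whatever care was received. That person did not disengage from needed care.

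Three consequences follow.

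- Positive screens are more often false at low scores, so low severity looks like a stronger barrier than it is.
- A depression code used as a predictor carries part of the outcome definition. If codes recorded after the index PHQ-9 are admitted, the outcome leaks directly into the model.
- The cut-off may mainly separate uncoded from coded Veterans, and then be applied to patients who meet an MDD criterion.

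A fourth arises if Aim 3 initiation is compared with the Aim 1 cohort rate, as Protocol A4c says (the SAP names a literature rate). That denominator includes Veterans who could not initiate, which lowers the comparator and favours the intervention.

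**Working it through.** The plan has no figure to reproduce: it gives neither the share of the cohort without a depressive disorder nor the Aim 1 initiation rate. All sizes below are therefore illustrations.

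**Step 1: logic.** Initiation requires a visit and a depression code. With no code, the probability of counting as non-engaged is exactly 1. Nothing in A4a removes evaluated Veterans without a depressive disorder or gives them their own category. The planned surveys of concordant and discordant cases look for unobserved barriers and leave the outcome rule unchanged.

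**Step 2: algebra.** Let f be the share of the cohort with no depressive disorder and e the initiation proportion in the rest.

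- Observed initiation = (1 - f) × e
- Share of the non-engaged who have no depression = f / (1 - (1 - f) × e)
- Amount by which the cohort rate understates e = f × e

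| e (assumed) | f (assumed) | Observed initiation | Share of non-engaged | Shortfall |
|---|---|---|---|---|
| 0.40 | 0.10 | 0.36 | 0.10/0.64 = 16% | 4 points |
| 0.40 | 0.20 | 0.32 | 0.20/0.68 = 29% | 8 points |
| 0.40 | 0.30 | 0.28 | 0.30/0.72 = 42% | 12 points |
| 0.27 | 0.10 | 0.243 | 0.10/0.757 = 13% | 2.7 points |
| 0.27 | 0.30 | 0.189 | 0.30/0.811 = 37% | 8.1 points |

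The 0.27 is the upper end of the range for any mental health care use in A1. It is not the Aim 1 rate.

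**Step 3: effect on the cut-off.** Simulation with N = 88,456, half for development and half for validation, a logistic score and a Youden cut-off. Assumed inputs:

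- PHQ-9 normal with mean 13 and SD 5, restricted to 10-27
- probability of true depression 0.60-0.75 at a score of 10, rising to 0.95 at 20
- 50-80% of true cases coded at the index date
- initiation 40-50% if coded
- true odds ratio for non-engagement about 0.83 per 5 PHQ-9 points
- one further predictor with log-odds SD 0.5

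Sensitivity for non-engagement among coded Veterans:

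| Scenario | Sensitivity |
|---|---|
| Code in score; false positives, and only 15-25% initiation in uncoded true cases | 3-30% |
| Code in score; lower initiation in uncoded cases, no false positives | 10-52% |
| Code in score; false positives alone, equal initiation | 17-42% |
| Code left out of score | about 56-65% (some runs as low as 51%) |
| Score and cut-off derived among coded Veterans | about 53-65% |

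With false positives present, about 20-35% of the non-engaged had no depression. The severity odds ratio per 5 points appeared as 0.62-0.74, against 0.80-0.85 among coded Veterans. That distortion remained when the code was left out.

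**Step 4: leakage from undated codes.** In a separate simulation, one covariate drove only diagnosis, another drove only engagement, and initiation was 40% among coded Veterans. Let u be the share never coded, which includes Veterans who never returned. At u = 10%, 30% and 50%:

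- The diagnosis-only covariate, with a coefficient near 0 among coded Veterans, took coefficients of -0.17, -0.37 and -0.56 in the full cohort.
- Entering a code from any time as a predictor gave AUCs of 0.69, 0.79 and 0.86, while AUC among coded Veterans stayed at about 0.63-0.64.

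At u = 50% the model passes the 0.8 mark that A4a uses for good fit, with no better discrimination among coded Veterans.

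**The case against.** The strongest reply has four parts.

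**The target is probable depression by design.** The plan argues that mild and subthreshold symptoms matter and that low severity lowers perceived need, so an association between low severity and non-engagement is its hypothesis. This stands as a reason to keep the full-cohort model. It does not justify labelling an evaluated Veteran without the disorder as non-engaged.

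**Many uncoded Veterans are true non-engagers.** Someone who screens positive and never returns is never coded. This stands. Under the assumptions above, 24-63% of truly depressed non-engagers have no index code, so refitting only in Veterans coded by the index date would discard much of the target.

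**The code may still vary in Aims 2 and 3.** A reader might infer that every Aim 2 and 3 participant has the code, so that the predictor becomes constant. The documents do not support that. Table 1 refers to ICD-9 chart codes. Table 2 refers to a DSM-5 MDD diagnosis, with no timing, and a phone screen assesses the Table 2 criteria. A newly referred patient could qualify without a prior code. The four Aim 2 provider stakeholders have no such criterion.

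**The consequence is limited.** The score selects 6 patients in Aim 2 and 15 in Aim 3, for formative work. This tempers the urgency, but the same score is presented as a first step towards an automated EHR tool.

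**Conclusion.** The concern holds in a bounded form. The outcome rule misclassifies Veterans evaluated and found not depressed, and the undated code predictors allow the score to learn part of the outcome definition. Both follow from the protocol's own wording.

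The size cannot be found from the documents. It is small if few cohort members lack the disorder: at f = 10% they make up 13-16% of the non-engaged for e of 27-40%. Under the wider simulation assumptions the share is about 20-35%.

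A reader might also infer that false-positive screens alone drive sensitivity among coded Veterans down to 3-30%. They do not. That range also needs an assumed lower initiation rate in uncoded true cases, which has no source in the documents and by itself gives 10-52%. False positives alone give 17-42%, and only if the code stays in the score. Without it there is little loss of sensitivity, though the severity effect is still exaggerated.

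This should be corrected before the score is used to select patients. It does not undermine Aim 1 as a whole.

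**What to change.** 1. Limit every predictor built on depression codes, including code-based chronicity, to dates on or before the index PHQ-9. Leave the depression-code flag out of the score that selects Aim 2 and 3 patients.
2. Do not count as non-engaged those Veterans who had a mental health or primary care evaluation after the index PHQ-9 with no depressive-disorder code; report them as a separate group. Keep as non-engaged those with no such visit. Define the evaluation in advance, since an unrelated primary care visit should not qualify.
3. Set the selection cut-off, and report AUC, sensitivity and specificity, in the subset that matches Table 2 (a depressive-disorder diagnosis or a mental health referral). State the timing of the diagnosis, which Table 2 leaves open. Report the full-cohort model alongside.
4. If the Aim 1 cohort rate is the Aim 3 comparator, compute it in that same subset. Reconcile this with the SAP, which names a literature rate.
5. Report the share of the cohort never coded and, within it, the share evaluated, so that the size of the problem can be seen.

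The cost is protocol wording and one re-run on data already extracted, with a smaller cohort for the cut-off. Veterans treated under another code, such as PTSD or anxiety, would fall into the separate group under item 2 and need a sensitivity analysis.
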